8.8.3 Laboratory Evaluations

All clinical laboratory data will be listed. Data for the following hematology, clinical chemistry, urinalysis and CSF laboratory (part 2 only) analytes (Table 7) will be summarized by dose cohort for Part 1 or treatment group for Part 2 and overall, and by visit. If data for any additional analytes are also recorded, then these will be listed only.

Table 7Clinical Laboratory Tests

Hematology	Clinical Chemistry	Urinalysis	CSF Analysis
			(Part 2)
Hematocrit Hemoglobin Mean corpuscular volume (MCV) Mean corpuscular hemoglobin (MCH) Mean corpuscular hemoglobin concentration (MCHC) Platelet count Red blood cell (RBC) count Red cell distribution width (RDW) White Blood Cell (WBC) Count including differential (neutrophils, lymphocytes, monocytes, eosinophils, basophils)	Alanine transaminase (ALT) Albumin Alkaline phosphatase Aspartate transaminase (AST) Bicarbonate Blood urea nitrogen Calcium Chloride Cholesterol Creatine kinase Creatinine Direct bilirubin Gamma-Glutamyl transferase (GGT) Glucose Lactate dehydrogenase Phosphorus Potassium Sodium Total bilirubin Total bilirubin Total protein Triglycerides Uric acid	Blood Glucose Ketones pH Protein Specific gravity Urine bilirubin	Total protein Glucose Red blood cells count White blood cells count Lymphocytes count Neutrophils count

All laboratory data will be reported in Conventional units. Out-of-reference-range values will be flagged as high (H) or low (L) in the listings.

For analysis purposes, values preceded by a "<" or a ">" sign (i.e. those below or above the limits of quantification) will be considered equal to the lower or upper limit of quantification, respectively.

Hematology and clinical chemistry data will be summarized for each dose cohort using standard descriptive statistics. Changes from baseline will also be summarized. Shift

CONFIDENTIAL

tables presenting movement in and out of reference range from baseline to each scheduled post-baseline visit will also be provided.

Number and percentage of subjects having any clinically significant laboratory value during post-baseline will be summarized for hematology, clinical chemistry, and urinalysis analytes. In addition, number and percentage of subjects having new-onset potentially clinically significant (PCS) laboratory values will be summarized. A PCS value is defined as a value that is out-of-reference-range. New-onset value for an analyte is defined as a PCS value for a subject following initiation of study treatment for which the subject did not have a PCS value for that analyte prior to initiation of study treatment. The denominator for calculating the percentage is the number of subjects without any PCS values at baseline and with at least one post-baseline assessment.

For each laboratory analyte, the baseline value will be defined as last scheduled or unscheduled value collected prior to the first dose of study treatment. Assessments carried out on day of first study treatment administration are considered to have taken place before the study treatment administration, if the corresponding times have not been recorded. For post-baseline, only data from scheduled visits will be included in the summary tables.

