## 15.11. Safety Endpoints

The safety analysis will be descriptive in nature. All safety data will be listed, and data will be tabulated by dose (Part 1) and treatment group (Part 2) where the data warrant. Safety data include:

- AEs, including assessment of lumbar infusion site
  - Events occurring prior to the first dose of investigational product or placebo will be defined as pre-treatment events.

- For Part 1, TEAEs will be defined as any AE occurring during or after the injection of study drug. This will therefore include all events occurring through Day 29/ET.
- For Part 2, TEAEs will be limited to those events occurring within 28 days after the last visit.

Incidence of AEs will be summarized for each treatment group/cohort by MedDRA system organ class (SOC) and preferred term, sorted in descending frequency by SOC, and then by preferred term within SOC. These summaries will be given by treatment in separate tables for each of the following TEAE event sets:

- All events
- Treatment related events (defined by a relationship to study drug of possible, probable, or definite).
- Serious adverse events
- Events leading to premature discontinuation from study
- Events by maximum severity
- AEs of Special Interest, ie, events relating to the lumbar puncture procedure (eg, infection, headache, back pain, excessive CSF leakage requiring blood patch).

Other safety outcomes will include:

- Clinical laboratory tests, including hematology, chemistry, metabolic, and urinalysis. Changes over time will be presented. Potentially clinically significant (PCS) ranges will be defined and used to determine the incidence of subjects experiencing newonset PCS laboratory values, where new-onset is defined as a PCS value for a subject following initiation of study treatment for which the subject did NOT have a PCS value for that analyte PRIOR to initiation of study treatment.
- Vital signs including: respiratory rate or pulse oximetry, heart rate, temperature, and blood pressure, as per the schedule of events. BMI will be assessed, with height collected only at screening.
- Physical examination
- 12-lead ECG. ECG parameters will be analyzed in a fashion similar to that of clinical laboratory parameters.

Condition-specific safety outcomes will include:

- ISNCSCI, GRASSP and all of the neurological measures evaluated for efficacy

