8.8.2 Adverse Events

All adverse events (AEs) recorded on the eCRF will be coded using the MedDRA dictionary [Version 22.0 (or a later version if updated during the study)] and classified as pre-treat AEs, or treatment-emergent AEs as follows:

- Pre-treat AEs are events that start prior to the date of first dose of study treatment;
- TEAEs are events with start date on or after the date of first dose of study treatment, or with a start date prior to the date of first dose of study treatment whose severity worsens on or after the date of first dose of study treatment. TEAEs will be limited to those events occurring within 28 days after the last injection of study treatment, with AEs occurring after that being defined as post-treatment. AEs with missing start date after applying imputation rules will be considered as TEAEs.

Assessment of AE severity will be based on the Common Terminology Criteria for Adverse Events (CTCAE, version 5.0). Missing severity will not be imputed.

The relationship between an AE and study treatment is assessed as definitely, probably, possibly, unlikely, or not related. A treatment-related AE is an AE considered by the investigator as definitely, possibly, or probably related to study treatment or with unknown/missing relationship to study treatment.

All AE data will be listed. Treatment-emergence status will be flagged in the listing. In addition, corresponding listings of serious AEs (SAEs), AEs leading to discontinuation from study, AEs of special interest, and AEs resulting in death will be produced. Summary tables of TEAEs by dose cohort for Part 1 or by treatment group for Part 2 and overall will be produced.

An overview table will summarize the number and percentage of subjects with at least one of the following TEAEs, where subjects with more than one TEAE in a particular category are counted only once in that category:

- Any TEAE;
- TEAE by maximum severity;
- Treatment-related TEAE;
- TEAE leading to discontinuation from study;
- TEAE of Special Interest;
- Serious TEAE;
- Treatment-related serious TEAE;
- Serious TEAE leading to discontinuation from study;
- Serious TEAE leading to death.

The number of total TEAEs will be also included in the overview table.

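### SAP 8.8.3 puts the limit for a potentially clinically significant laboratory value at the reference range, so the new-onset table ignores severity and carries an avoidable chance background

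*SAP*

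**What the plan says.** Protocol 15.11 leaves the limits to be set later: "Potentially clinically significant (PCS) ranges will be defined and used to determine the incidence of subjects" with new-onset values. SAP 8.8.3 then sets them: "A PCS value is defined as a value that is out-of-reference-range". It gives no multiple of the upper limit, no grade and no direction.

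The same section fixes the unit and the denominator of the table:

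- Unit: "New-onset value for an analyte is defined as a PCS value for a subject following initiation of study treatment", provided that the subject had no such value for that analyte before treatment.
- Denominator: "The denominator for calculating the percentage is the number of subjects without any PCS values at baseline and with at least one post-baseline assessment". Whether this applies to each analyte or across all analytes is not stated.

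SAP 8.8.3 also plans shift tables against the reference range at each scheduled visit, change-from-baseline summaries, listings with high and low flags, and a separate count of subjects with a clinically significant value, for which it states no criterion. Sections 9 and 10 of the SAP record changes to the planned analyses; neither mentions the PCS limit.

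The trial cites graded scales elsewhere. In SAP 8.8.2, "Assessment of AE severity will be based on the Common Terminology Criteria for Adverse Events (CTCAE, version 5.0"). Protocol 14.1.5 refers investigators to CTCAE for laboratory results, and protocol Table 13 gives moderate and marked thresholds for liver tests, adjusted for an abnormal baseline.

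**The concern.** Safety and tolerability are a primary objective of Part 2, and protocol 5.3 describes the study as the first evaluation of AXER-204 in humans. A PCS table should separate values that might matter from ordinary scatter around a reference limit. Under the SAP definition it cannot, because the label adds nothing to being out of range. The table tells the reader little that the shift tables do not, and it carries a background of chance flags in both arms. With about 16 subjects per arm, that background blurs moderate imbalances. The denominator wording adds a second difficulty: one possible reading removes most subjects from the table.

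**Working it through.** Neither document states an expected flag rate, so there is no planned figure to reproduce.

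**Inputs from the documents**

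- Post-baseline laboratory visits in Part 2: 5 (Days 21, 63, 104, 169, 253; protocol Table 6). Pre-dose samples: 2 (Screening, Day 1).
- Blood analytes in SAP Table 7: 14 hematology (9 tests plus 5 differential counts) and 22 distinct chemistry tests (total bilirubin is printed twice), 36 in all.
- About 16 subjects per arm.

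**Assumptions, not in the documents**

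- The chance *q* that an unaffected subject's value is out of range at one visit: 5%, with 2.5% and 1% as alternatives.
- Within-subject correlation between visits: 0 to 0.9.

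**Step 1. Chance flag for one analyte.** With independent visits the rate is 1 − (1 − *q*)^5:

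- *q* = 5%: 1 − 0.95^5 = 22.6%
- *q* = 2.5%: 1 − 0.975^5 = 11.9%
- *q* = 1%: 1 − 0.99^5 = 4.9%

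Independence overstates the rate. A simulation with both pre-dose values required to be in range gives:

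| Within-subject correlation | *q* = 5% | *q* = 2.5% |
|---|---|---|
| 0 | 22.7% | 11.9% |
| 0.5 | 15.3% | 8.4% |
| 0.7 | 10.3% | 5.8% |
| 0.8 | 7.7% | 4.3% |
| 0.9 | 4.7% | 2.6% |

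At *q* = 5% and 16 subjects at risk, that is between 16 × 0.047 = 0.8 and 16 × 0.226 = 3.6 flagged placebo subjects per analyte row.

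**Step 2. What the background does to a contrast.** Safety is descriptive here, so the power of Fisher's exact test serves only as a yardstick (16 per arm, two-sided 5%):

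| Background rate | Active 50% | Active 60% | Active 80% |
|---|---|---|---|
| 22.6% | 23% | 44% | 87.5% |
| 10% | 58% | 79% | 99% |
| 2% | 89% | 97% | about 100% |

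This isolates the effect of background. It does not forecast power after the fix, because a stricter limit would also lower the active-arm rate.

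**Step 3. The denominator.** If having no PCS value at baseline is read across all 36 analytes, the share of unaffected subjects who qualify at *q* = 5% is 0.95^36 = 15.8%, or 16 × 0.158 = 2.5 per arm. With an assumed between-analyte correlation of 0.3 it is about 28%, or 16 × 0.28 = 4.5 per arm. A per-analyte denominator avoids this.

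**Step 4. Numerator against denominator.** The numerator requires no PCS value at any time before treatment. The denominator looks only at baseline, which the SAP defines as the last value before first dose. A subject out of range at Screening and in range on Day 1 is counted in the denominator but can never enter the numerator. Under independence at *q* = 5%, that is 5% of each row's denominator.

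**The case against.** The protocol says only that PCS ranges will be defined. It does not say that they must differ from the reference range, so a reader who infers a broken promise goes further than the text. The SAP did define a limit; the criticism is of its quality and of its absence from section 9. That stands.

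A reader might also infer that almost every subject will be flagged by chance and that the table therefore cannot show a drug signal. The first part fits only a count of subjects flagged on any analyte. Over 36 analytes such a count would be about 73% to 100% at *q* = 5% and about 53% to 99% at 2.5%, depending on the correlations. But the SAP defines new onset for each analyte and specifies no pooled row. The second part fails because Part 2 has concurrent placebo, and Step 2 shows that a large imbalance on one analyte would probably be seen.

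Other displays also carry signal: change from baseline, shift tables, flagged listings, the separate clinically significant count, and laboratory abnormalities reported as adverse events and graded by CTCAE. This limits the consequence. It does not rescue the PCS table, which ignores severity whatever else is shown. The separate count is a weak substitute without a stated criterion.

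The shift tables are by visit and the PCS count is cumulative and restricted to new onset, so the two overlap without being identical. Finally, limits set too high could leave rows nearly empty at 16 per arm. That is a fair warning against using only the marked liver row, which would discard the protocol's own moderate row.

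**Conclusion.** The point holds as a weakness of one safety display. The PCS definition adds no information about severity, mostly restates the reference-range shifts, and is not logged as the choice that filled in the protocol's open item. Its chance background is about 5% to 23% per analyte over five visits at an assumed 5% per-visit rate, or about 3% to 12% at 2.5%, across within-subject correlations from 0.9 to 0. Those rates are assumptions; the lack of severity grading and the denominator faults do not depend on them. The documents do not support the conclusion that the laboratory data cannot reveal harm. The change should be made, since it concerns a primary objective and costs little.

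**What to change.** In SAP 8.8.3:

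1. Define PCS by analyte and direction from sources the trial already cites: a post-dose CTCAE v5.0 grade worse than baseline, with the sponsor to confirm the cut-off (for example grade 2 or higher), and both the moderate and the marked rows of protocol Table 13 for liver tests. These are reporting limits only and leave the protocol's management rules untouched.
2. Keep the present count, relabelled as new-onset out-of-reference-range. Analytes without a grade stay there.
3. State that the denominator is per analyte, and use one pre-treatment condition for numerator and denominator: either no qualifying value at any pre-dose sample, or none at baseline.
4. State the criterion for the separate clinically significant count.
5. Log the change. If it is adopted at this SAP version, which section 10 places after the Day 169 unblinding and before final lock, mark it as made after unblinding and show the new table beside the existing one.

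The cost is wording and a little programming, with no new data. The downside is that some analytes will have no PCS row and some rows may be sparse.

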### 14.1.5. Laboratory Assessments

The results of all laboratory tests required by the protocol will be recorded in the subject's eCRF. All clinically important abnormal laboratory tests occurring during the study will be repeated at appropriate intervals until they return either to baseline or to a level deemed acceptable by the Site Principal Investigator and the sponsor, or until a diagnosis that explains them is made. Abnormal laboratory test results that result in a change in study drug dosage or in discontinuation of the drug, or require intervention or diagnostic evaluation to assess the risk to the patient/subject, should be recorded as adverse events in the case report form. Investigators should review the CTCAE toxicity criteria that can be found at the following URL: https://ctep.cancer.gov/protocolDevelopment/electronic\_applications/docs/CTCAE\_v5\_Quick\_R eference\_8.5x11.pdf

All laboratory assessments will be collected as per the schedule of events (Table 5, Table 6).

The clinical laboratory tests analyzed in this study are provided in Table 12. The INRPTT, urine pregnancy testing and in-clinic safety laboratory tests requiring stat analysis will be processed locally. In addition, laboratory samples taken during Study Days 1-4 will be processed locally. All other laboratory tests will be analyzed by a central laboratory, **and the samples and urine samples will be collected and sent to the central laboratory on the day of** 

collection unless otherwise instructed. INR/PTT is required prior to the Day 1 lumbar puncture procedure with repeat INR/PTT tests on subsequent Study Days only if directed by the Principal Investigator. Clinical laboratory results will be reviewed by the study investigator when results are known prior to enrollment/randomization, and results available for each collection during the study including prior to discharge from the in-patient clinic in Part 1 of the study. During the course of the study, abnormal laboratory values should be repeated and subjects interviewed for evidence of clinical signs and symptoms consistent with the laboratory abnormality. Subjects with abnormal laboratories at screening can be rescreened (ie, lab repeated) for inclusion into the study within the 28-day screening window specified for labs. A Laboratory Manual will be provided separately for processing and shipping procedures.

Hematology	Serum Chemistry	
Hemoglobin	Glucose	Albumin
Hematocrit	Blood urea nitrogen	

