7.2 Visit Window (Part 2)

For part 2, time windows will be defined for both safety and efficacy assessments for summaries and values by visit as well as efficacy analysis. All data for unscheduled and scheduled visits have the potential to be included in the summary and analysis based on the actual date. The window for the visits following baseline will be constructed according to the following convention: the upper limit of the interval falls half way between the 2 visits if odd number of days exists between two consecutive visits. If an even number of days exists between two consecutive visits then the upper limit will be taken as the midpoint value minus 1 days. For example, the visit windows for ISNCSCI assessment are:

- Day 1, visit window NA
- Day 21, visit window 2 42
- Day 63, visit window 43 83
- Day 104, visit window 84 136
- Day 169, visit window 137 211
- Day 253, visit window 212 end of study

If there is more than one value within a visit window then the closest value to the scheduled visit date will be included in the summary and analysis. If 2 events are equal distance from the scheduled visit date then the event with earlier date will be selected for analysis. For listings, all visits including unscheduled visits will be displayed by collected visit name.

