8.8.5 Electrocardiograms

The following quantitative ECG measurements will be listed and summarized by dose cohort for Part 1 or by treatment group for Part 2 and overall, and by visit:

- heart rate (bpm);
- RR interval (msec), calculated as (60/HR)*1000;
- PR interval (msec);
- QRS interval (msec);
- QT interval (msec);
- Fridericia corrected QT (QTcF) interval (msec), calculated as $QT/\sqrt[3]{RR/1000}$.

Triplicate ECG will be taken in the study. Average values will be computed from available assessments from the triplicate ECGs to be used for data summaries.

The ECG measurements and changes from baseline in ECG will be listed and summarized using standard descriptive statistics.

An overall Investigator assessment of ECG will be listed and summarized as number and percentage of subjects with each assessment category by visit (categories: "normal", "abnormal, not clinically significant" and "abnormal, clinically significant").

Shifts from baseline (normal vs. abnormal, not clinically significant vs. abnormal, clinically significant) to the worst post-baseline interpretation will be presented.

The baseline value will be defined as last scheduled or unscheduled value collected prior to the first dose of study treatment. Assessments carried out on day of first study treatment administration are considered to have taken place before the study treatment administration, if the corresponding times have not been recorded. For post-baseline, only data from scheduled visits will be included in the summary tables.

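### In Part 2, the any-time laboratory counts and the worst-ECG shift use scheduled visits only, which conflicts with SAP 7.2 and with the tables' own definitions

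*SAP*

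**What the plan says.** SAP 8.8.3 plans several laboratory summaries. One is an any-time count: "Number and percentage of subjects having any clinically significant laboratory value during post-baseline will be summarized", covering hematology, chemistry and urinalysis. Another is a count of new-onset PCS values, where "A PCS value is defined as a value that is out-of-reference-range". The section then closes with "For post-baseline, only data from scheduled visits will be included in the summary tables".

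SAP 8.8.5 plans ECG shifts from baseline "to the worst post-baseline interpretation will be presented" and closes with the same scheduled-visits sentence.

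SAP 7.2, which applies to Part 2, states that "time windows will be defined for both safety and efficacy assessments for summaries and values by visit as well as efficacy analysis". It adds: "All data for unscheduled and scheduled visits have the potential to be included in the summary and analysis based on the actual date". Its selection rule is: "If there is more than one value within a visit window then the closest value to the scheduled visit date will be included".

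Protocol 14.1.5 says that during the study "abnormal laboratory values should be repeated and subjects interviewed for evidence of clinical signs and symptoms", and it asks for moderate liver abnormalities to be repeated within 1 to 2 days. Protocol 14.1.4 allows ECG time points to be added if indicated. The Part 2 follow-up text (Synopsis and 7.1.2.3) allows a clinic evaluation after the Day 137 telephone call.

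**The concern.** A scheduled-visits rule is reasonable for means and shifts by visit, where each subject should contribute one comparable value per time point. It does not suit a table defined over the whole post-baseline period. A count of any abnormal value, or a worst reading, that leaves out part of the follow-up is not what its title says.

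There is also a plain conflict for Part 2. SAP 7.2 makes unscheduled safety results eligible, and 8.8.3 and 8.8.5 bar them. Section 7.2 has no clause giving way to later sections, so two programmers could build different tables from the same plan.

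Safety and tolerability are a primary objective of Part 2. Results outside the schedule would still be listed, but a listing gives no count by arm.

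**Working it through.** No stated trial figure is at issue. The check sets the sections side by side, with some date arithmetic.

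**1. Are unscheduled Part 2 results eligible under SAP 7.2?** Table 6 of the protocol schedules post-baseline blood laboratory tests on Days 21, 63, 104, 169 and 253. These are also the ISNCSCI days used for the worked example in 7.2. The 7.2 convention gives these upper limits:
- 21 to 63: 63 − 21 − 1 = 41 days between (odd), midpoint 42, upper limit 42.
- 63 to 104: 40 days between (even), midpoint 83.5, upper limit 83.
- 104 to 169: 64 days between (even), midpoint 136.5, upper limit 136.
- 169 to 253: 83 days between (odd), midpoint 211, upper limit 211.

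This reproduces the SAP's own windows: 2–42, 43–83, 84–136, 137–211 and 212 to end of study. They leave no gap, so every unscheduled blood result after Day 1 is eligible under 7.2 and barred under 8.8.3.

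**2. How much follow-up lies between scheduled tests?** The intervals between laboratory days, starting from Day 1, are 20, 42, 41, 65 and 84 days. ECGs are also scheduled on Days 42 and 84, but the last two intervals (65 and 84 days) are the same for both.

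**3. In which direction can the rule act?** A subject counts in an any-time table if at least one value qualifies, and a worst reading is a maximum over readings. Removing values can lower either or leave it unchanged. It cannot raise the number of subjects counted.

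The new-onset table is also asymmetric. Section 8.8.3 lets the baseline come from an unscheduled sample, so such a sample can remove a subject from the denominator. An unscheduled post-dose abnormality cannot add a subject to the numerator. Protocol 15.11 defines new onset by timing after the start of treatment, with no limit to scheduled visits, and SAP section 9 does not list the restriction as a change.

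**4. Which results are lost?**
- A repeat that follows an out-of-range scheduled value does not change the PCS count, because the subject is already counted for that analyte.
- A repeat that first becomes clinically significant is lost from the any-time count.
- An abnormality first found at an unscheduled visit is lost from the any-time and new-onset counts.
- An added ECG with a worse reading than any scheduled one is lost from the worst-case shift.

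**5. Would applying 7.2 alone cure this?** No. It keeps one value per window. Suppose the scheduled draw is s days from target and the repeat comes r days later. The repeat is selected only if |s + r| < |s|; ties go to the earlier date.
- Visits with a ±5-day window: r = 1 needs s from −5 to −1, which is 5 of 11 offsets. r = 2 needs s from −5 to −2, which is 4 of 11.
- Visits with a ±7-day window: 7 of 15 for r = 1 and 6 of 15 for r = 2.

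When the repeat is selected, it replaces the scheduled value, so one of the two is always dropped.

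**6. Do the adverse event tables fill the gap?** Only in part. Under Protocol 14.2.2 an abnormal result is an adverse event only if it meets stated criteria. SAP 8.8.2 limits treatment-emergent events to 28 days after the last injection, nominally Day 104 + 28 = Day 132, which is before the nominal Day 137 call. Visit windows can make these overlap: a last dose on Day 109 gives Day 137, and the call may come from Day 130.

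**The case against.** The other side has real points, and most of them limit the size of the problem.

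- **Repeats rarely matter for PCS.** They are ordered because a value was already abnormal. This stands for the PCS count, though not for a repeat that first becomes clinically significant.
- **Important findings reach the adverse event tables by arm.** Protocol 14.1.4 and 14.1.5 send clinically significant ECG findings and qualifying laboratory abnormalities there. This stands as a partial backstop, limited as in step 6 above.
- **Section 7.2 says only that unscheduled data have the potential to be included, so 8.8.3 may override it.** That reading is possible, but the SAP does not say so. It would also leave the any-time and worst-case tables at odds with their definitions.

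A reader might also infer four stronger claims that the documents do not support:
- That symptom-driven tests ordered by the protocol are discarded. The only item the protocol calls symptom-driven is the abbreviated physical examination (14.1.3). Repeat laboratory tests are ordered; extra ECGs are only permitted.
- That blood drawn on dosing Days 42 and 84 is excluded. Laboratory blood tests are not planned then, but both are scheduled visits, and the rule refers to data from scheduled visits.
- That Part 1 has the same conflict. SAP 7.1 already says unscheduled Part 1 data are listed only, unless specified otherwise.
- That the vital-sign tables in 8.8.4 are affected in the same way. They are by time point, with no any-time or worst-value table.

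**Conclusion.** The point holds for Part 2. The closing sentence of SAP 8.8.3 and 8.8.5 conflicts with 7.2, and it defeats the stated purpose of the any-time clinically significant, new-onset PCS and worst-ECG tables. The resulting bias in the counts is downward or nil.

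Its size cannot be estimated, because the documents do not say how many unscheduled tests will occur or how many will show a first abnormality. For scale only, one subject in an arm of about 16 is 1/16 = 6.25 percentage points, and more where the new-onset denominator is smaller. That is not an estimate of how many subjects would be missed. A large distortion of the safety results might be inferred, but the repeat-test logic and the adverse event route point to a small one.

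The conclusion assumes that the scheduled-visits sentence means what it says for every summary table in its section.

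**What to change.** For Part 2, amend SAP 8.8.3 and 8.8.5 as follows:
- Limit the scheduled-visits sentence to by-visit descriptive and shift tables, and reconcile it with 7.2 so that one stated rule governs which value represents a visit.
- Add a separate rule that the any-time clinically significant, new-onset PCS and worst-post-baseline ECG tables use every post-dose result, scheduled or unscheduled, and are not subject to the one-value-per-window selection in 7.2.

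Section 8.8.4 needs only the same reconciliation with 7.2.

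The cost is wording and a small programming change; SAP 8.8.3 and 8.8.5 already provide for listing the results. SAP section 10 shows that some sponsor staff had seen unblinded Day 169 results, and 2.2 planned safety summaries at that stage. The change should therefore be dated and documented as made after that unblinding and before final database lock, with a rerun of any Day 169 safety tables already produced.
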